All participants will complete the website questionnaires in order to standardize collection of our functional outcomes. Practitioners in both arms will not have access to the responses to the patient satisfaction questionnaires (WAI-SR and CSQ-8). The other questionnaire responses of the participants randomized to REVAMP management will be available to the practitioners performing the phone clinic evaluations. Enrolled subjects assigned to the in-person arm will only have access to the website's questionnaires but none of its other features. They will be informed that a research staff member will contact them to schedule their first clinic appointment. None of the questionnaires they complete on the website will be shared with their practitioners. At the time of their in-person clinic visits, these participants will complete the questionnaires that are routinely used as a part of the clinical site's usual care. That information will not be collected for analysis.

**Table 2.** Data collection and action schedule for all participants

Measures & Procedures	Baseline assessment	Initial clinical assessment	AutoCPAP set-up	1-week phone FU	1-month FU assessment	3-month FU assessment
	Week 0	Week 2-4	Week 8	Week 9-12	Week 12	Week 20
Eligibility criteria	In-person					
Informed consent	In-person					
Patient characteristic questionnaire	website					
Functional & QOL questionnaires†	website				website	Website Δ
Therapy process indicators‡		website		website	website	Website Δ
Clinical assessment*		In-person vs phone		Phone	In-person vs phone	In-person vs phone
APAP set-up			DME			
APAP adherence*				Wireless	Wireless	Wireless

DME = home health care company; FU=follow-up; QO =quality of life; Δ=performed every 3 months thereafter to the end of data collection

\* Subjects randomized to in-person management will have in-person clinic evaluations in the sleep center and subjects randomized to REVAMP management will have phone clinic sessions. APAP adherence in both groups will be obtained by wireless modem.

[figure not shown]
† Functional & QOL questionnaires: FOSQ-10, ESS, SF-12, CES-D, and EQ-5D; ‡ Therapy process indicators: WAI, CSQ-8 (performed within 1-week following each encounter)

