All practitioners will have access to the participant's daily APAP data at the manufacturer's HIPAA compliant, password protected web-site (EncoreAnywhere, Philips-Respiration, Inc or AirView, ResMed, Inc). Participants in the REVAMP arm and their practitioners will also be able to view the PAP data on the REVAMP website. When clinically indicated, adjustments to the APAP pressure range will be made either at the time of the in-person clinic visit or by entering this modification on the manufacturer's website that will reset the participant's APAP device by transmitting the information to the home unit via the wireless connection. Participants will be informed if the pressure range is adjusted. Subjects who unable to tolerate APAP or refuse treatment will be seen by a sleep physician for further evaluation and management.

Blinding of research personnel. Given the differences in management of the two groups, the research personnel cannot be blinded to a participant's group assignment. The practitioners delivering care will not be involved with scoring the HSTs and all of the participant questionnaires are self-administered. The practitioners will not have access to the patient satisfaction questionnaire results or to the data collected for Aims 2 and 3.

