who are CMS beneficiaries will be obtained by submitting a standard request to the VA Information Resource Center (VIREC) to access the VA/CMS repository data that is also available on the CDW. Non-VA and non-CMS services not captured by VA database inquiries will be derived from patient self-reported data collected on questionnaire. The latter service use will be costed out using data that will be derived from the cost data at the respective sites as well as Federal reimbursement schedules when that medical center's cost data are not available. Participants will be asked to provide details about any traffic accidents and we will cost them out using published data on the cost of such accidents. Costs of wireless PAP data transmission, when applicable, will be included in the analysis. [name], our database manager, has strong experience working in VINCI and with SQL server output tables to create SAS datasets.

Preference-weighted QOL. As recommended by the Panel on Cost-effectiveness in Health and Medicine, QALYs will be assessed using preference-weighted generic quality of life instruments. Preference-weighted health-related quality of life will be expressed in terms of the SF-6D (primary preference measure calculated by use of the SF-12 scoring algorithm), and the EQ-5D (secondary preference measure). We propose use of both the SF-6D and EQ-5D for secondary analyses of treatment differences because prior research has indicated that patients with OSA provide significantly different responses to these 2 instruments. While there is little information available for identifying which is a better measure of preference-weighted QOL, either in general or specifically for OSA and its treatment, Schmidlin et al. have recommended use of the SF-6D and the EuroQOL feeling thermometer for the evaluation of OSA treatments.

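### EQ-5D, SF-12 and self-reported service use are open to REVAMP practitioners in one paragraph and, as Aim 2 data, closed to all practitioners in another

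*Combined protocol and SAP*

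**What the plan says.** The combined protocol and SAP deals with practitioner access to questionnaire answers in two places.

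The paragraph on website questionnaires, just before Table 2 under Aim 1, names two withheld instruments: "Practitioners in both arms will not have access to the responses to the patient satisfaction questionnaires (WAI-SR and CSQ-8"). For the REVAMP arm it then continues: "The other questionnaire responses of the participants randomized to REVAMP management will be available to the practitioners performing the phone clinic evaluations". For the in-person arm it says: "None of the questionnaires they complete on the website will be shared with their practitioners". In-person participants fill in their site's usual forms at clinic visits, and of those the plan says: "That information will not be collected for analysis". The same paragraph gives standardized collection of the functional outcomes as the reason for using the website.

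The paragraph headed Blinding of research personnel accepts that staff cannot be blinded. It offers as safeguards that practitioners do not score the sleep tests, that questionnaires are self-administered, and that access is limited: "The practitioners will not have access to the patient satisfaction questionnaire results or to the data collected for Aims 2 and 3". No arm is named.

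**The concern.** The trial is unblinded and many of its outcomes are self-reported, so the statement on restricted access carries weight. If the website is configured as the questionnaire paragraph describes, that safeguard is not delivered in the REVAMP arm for the instruments that produce the QALYs. The treating practitioner could read the analysed form in one arm and not in the other.

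People who know that their clinician will read a reply may answer differently, either playing up benefit or playing up problems to get help. If that happened, it would enter the between-arm difference in preference scores and hence the QALY difference and the cost-effectiveness ratio of Hypothesis 2b. These are secondary outcomes of Aim 2. The Aim 2 primary outcome is sleep-related cost, and its VA component comes from administrative data that the audience for a questionnaire cannot touch.

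**Working it through.** **Step 1: what is open in the REVAMP arm.** Everything on the website except WAI-SR and CSQ-8. The Table 2 footnote lists the rest of the repeated battery: "Functional & QOL questionnaires: FOSQ-10, ESS, SF-12, CES-D, and EQ-5D". The baseline list under Aim 1 adds a website form on medical service use not captured by the medical record. The Aim 2 section says such self-report is also collected by questionnaire, without stating the mode after baseline.

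**Step 2: what counts as Aim 2 data.** The Aim 2 measures section covers utility as well as cost and points to the questionnaires in Appendix 3. It names "SF-6D (primary preference measure calculated by use of the SF-12 scoring algorithm") and makes EQ-5D the secondary preference measure. It takes non-VA, non-CMS service use from patient self-report.

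**Step 3: side by side.**

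| Form | Role | REVAMP practitioners, questionnaire paragraph | All practitioners, blinding paragraph | Conflict |
|---|---|---|---|---|
| EQ-5D | Aim 2 only | open | closed | yes |
| SF-12 | Aim 2 through SF-6D; also Aim 1 secondary | open | closed as Aim 2 data | yes, with a dual role |
| Self-reported service use | Aim 2 costs | open | closed | yes |
| FOSQ-10, ESS, CES-D | Aim 1 | open | not mentioned | no |
| WAI-SR, CSQ-8 | Aim 3 | closed | closed | no |

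For in-person practitioners every row is closed, so the conflict lies in the REVAMP arm alone.

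**Step 4: can the analysis absorb a reporting difference?** Under Participant randomization, allocation follows completion of the baseline questionnaires. Baseline answers are therefore given before the arm is known, and only the 1-month, 3-month and later answers can differ by audience. A baseline covariate cannot remove a shift that begins after allocation. The planned sensitivity analyses concern missing data and the analysis population, not this.

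**Step 5: scale for the QALY analysis.** The documents give no size, direction or SD for the preference scores, so no bias can be estimated. They do give a yardstick. The 3-month sleep-related costs assumed for power in Aim 2 (from the prior home versus in-lab study) differ by 2538 − 1755 = $783. At the plan's threshold of $100,000 per QALY, that equals 783/100,000 = 0.0078 QALY. Over 0.25 year this is 0.0078/0.25 = about 0.031 on the preference scale, if held throughout. A shift of that size would be worth as much as the whole assumed cost difference. Nothing in the documents says that such a shift will occur.

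**Step 6: FOSQ-10, purely illustrative and for Hypothesis 1a alone.** With SD 2.80 and 114 per group, SE = 2.80 × √(2/114) = 0.371. Power = Φ(1/0.371 − 1.645) = 85.3%, which reproduces the plan's 85%. Suppose REVAMP answers shifted by b points:
- in favour of REVAMP, one-sided error at a true difference of −1 is Φ(b/0.371 − 1.645): 8.5% for b = 0.10 and 16.6% for b = 0.25;
- against REVAMP, power at a true difference of 0 is Φ((1 − b)/0.371 − 1.645): 64.7% for b = 0.25.

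Both values of b are assumptions. The plan also requires Hypothesis 1b to be met, and APAP hours are recorded wirelessly. The error figures are therefore upper limits on a false overall conclusion of non-inferiority under the assumed shift.

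**The case against.** Four arguments can be made on the other side.

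First, data collected for Aim 2 might mean costs only. The Aim 2 measures section does not allow this, since it includes the utility instruments. Self-reported service use would remain exposed even on that reading.

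Second, SF-12 is listed among the Aim 1 measures and analysed as an Aim 1 secondary outcome, so the blinding paragraph may not have been meant to cover its raw answers. This stands in part: the conflict is less clean for SF-12 than for EQ-5D. The same items still generate the primary preference measure.

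Third, practitioner viewing may belong to the REVAMP pathway, and in-person clinicians have their own usual-care forms. This is a fair explanation of why access differs. It does not make the two paragraphs agree.

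Fourth, the documents do not say that participants in either arm are told who reads their answers, and the text under review does not include the consent form. An effect of audience on answers is therefore possible, not shown. This stands in full.

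A reader might go further and infer that the FOSQ-10 comparison is biased and the error rate for Hypothesis 1a inflated. The documents do not support that. The blinding paragraph promises nothing about FOSQ-10, so there is no contradiction for it. The direction and size of any shift are unknown, and the unequal access may be part of the intervention being tested.

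**Conclusion.** The contradiction is certain for EQ-5D. It also holds for SF-12 through SF-6D and for the website form on service use. As written, a stated safeguard of an unblinded trial is missing in one arm for self-reported inputs to the secondary QALY and cost-effectiveness analyses. The pre-allocation baseline cannot adjust for any reporting difference that results.

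That a reporting difference exists is an assumption. It requires participants to know or suspect who reads their answers, and its size and direction cannot be obtained from the documents. The figures in the working are scales, not estimates.

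For FOSQ-10 the finding is limited to an explicit asymmetry of access that should be acknowledged. It is not evidence that the non-inferiority test is invalid.

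**What to change.** Reconcile the two paragraphs by adding EQ-5D, SF-12 and the self-reported service-use form to the questionnaires withheld from practitioners in both arms, at every time point. Show participants in both arms the same on-screen statement of who will see each set of answers.

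For FOSQ-10, record the unequal access as a limitation of the Hypothesis 1a comparison. Hiding only the month-3 FOSQ-10 would not be a clean remedy. The month-1 score enters the mixed model and the last-observation-carried-forward analysis, and would still be visible in one arm. Hiding FOSQ-10 altogether might change the pathway under test.

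The cost is a display setting on the website and a few lines of protocol text. The downside is that REVAMP practitioners lose sight of the three forms. If the sponsor regards that visibility as part of REVAMP care, the blinding paragraph must instead be corrected, and the same limitation stated for the QALY and cost-effectiveness results.

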## RESEARCH DESIGN AND METHODS

### Aim 1 Effect of REVAMP management compared to in-person care on functional outcomes

Study population and enrollment of participants. Veterans (n=356) referred to one of the sleep centers for evaluation of OSA will be recruited. Men and women will be included with no restrictions based on race and ethnicity. We will target women's clinics to enhance the recruitment of women. Healthcare providers submitting referrals will be asked on the CPRS consult form whether or not the patient is interested in participating in the study. Interested patients will be contacted by phone by the study coordinator to explain the study and determine if they have internet access and are eligible based on the inclusion/exclusion criteria. Eligible patients interested in participation will be scheduled to meet with the study coordinator to obtain signed informed consent. Patients who are ineligible or decline to participate will be scheduled for a routine initial clinic appointment. Enrolled participants will be given the uniform resource locator (url) address to the REVAMP website and a user name and temporary password. The participant's primary care provider will be informed that his/her patient is enrolled in the study and that all clinically indicated care should continue to be provided.

Eligibility criteria and enrollment. Veterans must meet the following inclusion criteria prior to enrollment:

1. Age  $\geq$  18 years and enrolled at one of the participating VAMCs
2. Referral to one of the participating sleep centers for evaluation of suspected OSA
3. Access in the home to the internet, e-mail, and phone on all days
4. *Living within a 45 miles radius of the clinical site so that participants randomized to in-person delivery of care will be able to travel to and from the sleep center*
5. Fluent in English as assessed on the initial phone contact

Individuals will be excluded from the study for the following reasons:

1. Unable or unwilling to provide informed consent and complete required questionnaires
2. Previous diagnosis of OSA, central sleep apnea ( $\geq$  50% of apneas on diagnostic testing are central apneas), Cheyne-Stokes breathing, obesity hypoventilation syndrome, or narcolepsy
3. Previous treatment with PAP, non-nasal surgery for OSA, or current use of supplemental oxygen

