4. A clinically unstable medical condition in the previous 2 months as defined by a new medical diagnosis (e.g., pneumonia, cardiac disease, thyroid disease, depression or psychosis, cirrhosis, cancer, etc.)
5. Individuals who regularly experience jet lag or irregular work schedules over the previous 3 months
6. Women who are pregnant or women who are sexually active and of child-bearing age who are not using some form of contraceptive
7. *Unable to perform tests due to visual (inability to read the consent form) or hearing (unable to have a phone conversation) impairment, or unable to perform activities of daily living*

Participants will complete the following baseline questionnaires on the website: FOSQ-10, EES, SF-12, CES-D, EQ-5D (including the EuroQol feeling thermometer), and medical service use not captured by their electronic medical record (Table 2 and Appendix 3). The Charlson comorbidity index will be used to determine if health status predicts which patients are good candidates for REVAMP management.

To monitor for possible selection bias, all potential participants will be tracked to determine the number who agree to be contacted, the number who provide informed consent, the criteria that excluded an individual's participation, and the reasons why participants were unable to complete the protocol. Post-hoc analysis will compare patient characteristics at baseline to assess for any differences across groups and sites. Following completion of the baseline questionnaires, the CES-D score will be reviewed by a member of the research team who is not involved with delivery of care. The participant's primary care provider will be notified if the CES-D score is greater than 24, indicating the presence of severe depression. These participants will be allowed to continue in the study since all participants with OSA will receive APAP treatment and this intervention has been shown to improve depression. To assess for any medication changes that might affect functional outcomes, a list of the participant's medications, with their dosage and frequency, will be obtained from the patient and the patient's medical record during the first 3 months of PAP treatment.

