**Participant randomization.** Upon completing baseline questionnaires, a computer-generated, blocked randomization scheme in the REVAMP program will automatically allocate eligible participants into one of two groups: *REVAMP management versus in-person management*. Randomization at each site will be programmed by SAS module Proc Plan. Block size at each site will be six subjects so that among each block of six randomized individuals, exactly three will be assigned to each group in a random order. Investigation and management of the two arms of care will be conducted over equal time periods.

**REVAMP pathway.** Following completion of the website questionnaires and the HST, REVAMP participants will be scheduled for an initial phone interview with the *sleep specialist (MD or NP)* (Fig 4). The practitioner will review the results with the subject. *Using the criteria required by the Center of Medicare and Medicaid Services, participants with AHI  $\geq 15$  events/hr and subjects with  $5 \leq AHI < 15$  who have OSA-related symptoms will be diagnosed with OSA.* Those interested in PAP treatment will be prescribed an APAP unit with wireless modem. Subjects with OSA who are found on follow-up to require bilevel PAP and/or supplemental oxygen will continue to participate in Aim 1. Participants testing negative for OSA will be offered usual clinical care to further evaluate their sleep-related symptoms. Participants with a diagnosis of central sleep apnea/Cheyne-Stokes respiration

(CSA/CSR) will be referred to a sleep physician and PSG testing. *Participants without OSA on HST and participants with CSA/ CSR will not be included in the Aim 1 modified intent to treat analysis set but will be included in the primary analysis set of Aim 2 and Aim 3.*

The wireless modem on the home PAP unit sends PAP data daily to the manufacturer's server which in turn exports the data daily to the REVAMP website. The website displays the following information in an easily understandable format: hours of use, amount of air leak, and AHI (Fig. 2). Participants and practitioners can view the data on the REVAMP website. Participants will be instructed to review their results on the website daily. The number of times a subject logs into the website will be tracked.

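### The fixed, printed block size of six within each site allows up to a quarter of allocations to be known in advance; varied, undisclosed blocks would cut that sharply at little cost

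*Combined protocol and SAP*

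**What the plan says.** The paragraph on participant randomization (Aim 1) sets out a scheme blocked by site: "Randomization at each site will be programmed by SAS module Proc Plan". It then says "Block size at each site will be six subjects", so that in each block "exactly three will be assigned to each group in a random order". Allocation happens once the baseline questionnaires are complete, when "a computer-generated, blocked randomization scheme in the REVAMP program will automatically allocate eligible participants into one of two groups".

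The paragraph on blinding states that "the research personnel cannot be blinded to a participant's group assignment". Recruitment comes before allocation. In the paragraph on study population and enrollment, "Interested patients will be contacted by phone by the study coordinator to explain the study" and check eligibility; then "Eligible patients interested in participation will be scheduled to meet with the study coordinator to obtain signed informed consent".

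The plan does consider selection. Under the eligibility criteria it says "To monitor for possible selection bias, all potential participants will be tracked", and it compares baseline characteristics across groups and sites. Nothing in the text says that block size varies, that it is kept from site staff, or who can see the running sequence of assignments.

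**The concern.** Automatic allocation hides the list but not the arithmetic. When every block at a site holds three of each arm, anyone who has counted three of one arm within a block knows the rest of that block. The protocol prints the number needed to do the counting. Planned accrual of 6 patients per month per site makes a block last about one month, which is easy to follow.

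The steps before allocation leave room for discretion: whom to phone next, when to schedule consent, and how to judge criteria such as English fluency by phone or a clinically unstable condition. If the next arm is known, those choices can be tilted, deliberately or not, toward patients thought to suit it. Both hypotheses tested for non-inferiority, change in FOSQ-10 and APAP hours, concern outcomes that plausibly depend on motivation and ease with technology. Selection favouring REVAMP would push toward a false claim of non-inferiority; selection the other way would cost power.

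**Working it through.** **The plan's own figures.** Inputs from the section on sample size and power: margin 1.0 FOSQ point, SD 2.80, one-sided alpha 0.05, power at least 85%. A noncentral t calculation gives 84.9% at 113 per group and 85.2% at 114, so 114 is reproduced. With 20% lacking OSA and 20% dropout, 228/(0.8 × 0.8) = 356.25, against the stated 356. That is about 119 per site, or 119/6 ≈ 19.8 blocks. The documents give no predictability figure.

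**Certain prediction, fixed blocks of six.** A 3:3 block has 20 possible orders. For an observer with full knowledge:
- positions 1 to 3 are never certain;
- position 4 is certain if the first three match: 2/20 = 1/10;
- position 5 is certain if three of the first four share an arm: 8/20 = 2/5;
- position 6 is always certain.

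The sum is 0.1 + 0.4 + 1 = 1.5 of 6, or 25%, which agrees with the closed form 2b/(b + 1) at b = 3. Applied to 356, the ceiling is 89 allocations. At a site of 119 (19 full blocks plus 5), it is (19 × 1.5 + 0.1 + 0.4)/119 = 29/119 = 24.4%.

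**If the observer is behind.** With the latest assignment unknown, the certain positions shift by one: (1/10 + 2/5)/6 = 8.3%. With two unknown: (1/10)/6 = 1.7%. With three unknown: 0%.

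**Best guess, fixed six.** Always guessing the arm that is behind gives 3 + (2^5/20 − 0.5) = 4.1 correct of 6, or 68.3%, where 50% means no information.

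**Randomly varied blocks.** These figures come from 4,000 simulated lists of 119 per site. The observer knows the set of sizes (equally likely) and all past assignments, but not the size in use. The sets are assumptions; the documents name none.

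| Block sizes | Certain in advance | Best guess correct |
|---|---|---|
| 6 (as planned) | 24.4% | 68% |
| 4, 6 | 5.5% | 69% |
| 6, 8 | 3.9% | 67% |
| 4, 6, 8 | 2.3% | 68% |
| 2, 4, 6 | 4.1% | 70% |
| 4, 8 | 7.4% | 68% |
| 2, 4 | 11.0% | 72% |

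**Cost in balance and power.** With sizes 4, 6 and 8, the largest difference between arms at a site was 3, against 1 with fixed six. By the normal approximation, power at 228 analysed is 85.35% at 114/114, 85.31% at 110/118 and 85.15% at 105/123.

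**What steering could do (illustration only).** Assume that patients enrolled with REVAMP foreseen would improve 1 FOSQ point more than those enrolled with in-person care foreseen; the documents offer no such figure. The standard error is 2.80 × √(2/114) = 0.371. With 25% foreseen, the bias is 0.25 point and the one-sided error at the margin is Φ(0.25/0.371 − 1.645) ≈ 17% instead of 5%. With 8.3% foreseen it is about 8%; with 2.3% it is about 6%. This counts only certain predictions, not steering on guesses.

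**The case against.** The strongest reply is that nobody at a site may hold the knowledge that the 25% requires. Randomization fires when the participant finishes the online questionnaires, not when the coordinator schedules or consents. With several consented patients pending, the coordinator does not control who takes the next slot and may not know the latest assignments. Being open to a participant's assignment is also not the same as seeing an ordered list of all assignments. This stands: 25% is a ceiling, and a short lag shrinks it quickly.

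The plan also has safeguards. It tracks everyone approached and compares baseline characteristics. It accounts for site and baseline FOSQ, names age, sex and race as possible confounders, and repeats the primary tests with adjustment for imbalanced factors associated with FOSQ change. Home internet access and the 45-mile limit narrow the scope for steering, and APAP hours are recorded by modem. These measures can detect or partly correct selection, but they do not prevent it, and adjustment reaches only measured factors.

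A reader might infer that staff do foresee a quarter of allocations, or that the result will be biased. The documents support neither: they show no steering, and they do not say what staff see. A reader might also infer that varied blocks would remove the problem. They would not, and the 68% guess rate is no argument for them, because it hardly moves.

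**Conclusion.** The weakness is real, preventable and modest. A fixed block size, printed in the protocol and applied within site in an open trial, allows up to 25% of allocations to be certain in advance. That assumes knowledge of the block starts and all earlier assignments at the site; with one or two assignments not yet known, the figure is 8.3% or 1.7%. Where this trial lies between those values cannot be settled from the documents. The effect on FOSQ-10 or APAP hours is likewise not established, and the error rates above rest on an assumed selection effect.

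The point is a cheap improvement to the design, not an error or contradiction in the plan.

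**What to change.** Program PROC PLAN with randomly varied block sizes within each site, for example 4, 6 and 8. Avoid sets built on very small blocks: 2 and 4 leave 11.0% certain and raise the best-guess rate to 72%. Move the block sizes out of the protocol into a restricted randomization document, and state that personnel who screen, schedule or consent have access to neither the sizes nor the list. State also who may see the running sequence of assignments. If enrollment has started, apply the change to the blocks not yet opened.

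The work is a few lines of code and a short text change. The downside is the slightly larger possible imbalance at the end of the trial. The power loss of 85.35% − 85.15% = 0.2 percentage points is for a 105/123 split, a difference of 18; three sites each at the largest simulated difference of 3 would give 9.
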